9.2.4 Informed Consent and Enrollment

Any patient who provides informed consent (i.e., signs and dates the informed consent form and assent form, if applicable) is considered enrolled in the study. A legally authorized surrogate may also sign the informed consent. If the patient is deceased or lost to follow-up, only anonymized data will be collected from the medical chart and entered into the electronic data capture (EDC) system.

9.2.5 Subject Identification Code

The following series of numbers will comprise the subject identification code (SIC): protocol identifier 241302 to be provided by the MAH, two- or three-digit study site number (e.g., 02) to be provided by the MAH, and three- or four-digit subject number (e.g., 0003) reflecting the order of enrollment (i.e., signing the informed consent form [ICF]). For example, the third subject who signed an ICF at study site 02 will be identified as Subject 161302-020003. All study documents pertaining to the subject (e.g., case report forms [CRFs], clinical documentation, etc.) will be identified with the SIC.

Alternative uniquely coded SIC(s) is permitted as long as it does not contain a combination of information that allows identification of a subject (e.g., collection of a subject's initials and birth date would not be permitted), in compliance with laws governing data privacy.

9.2.6 Screening and Follow-up

The study site is responsible for maintaining an enrollment/screening log that includes all subjects enrolled. The log also will serve to document the reason for screening failure or decision to not enroll. All screening data will be collected and reported in CRFs, regardless of screening outcome. If a subject is re-screened, the End of Study CRF should be completed, and a new ICF, new SIC and new CRF are required for that subject.

The overall study design is illustrated in Figure 1.

Figure 1
Study Design for Baxalta Non-Interventional Study Protocol 241302

Obizur [antihemophilic factor (recombinant), porcine sequence]
prescribed by a physician

ective data collection if treatment prior to study initiation (with ontion

- Retrospective data collection if treatment prior to study initiation (with option for follow-up duration: 180 days post-treatment); enroll at first clinic visit
- Prospective data collection (duration: 180 days) if treatment on or after study initiation; up to five days to enroll from treatment initiation

[figure not shown]

Table 1. **Schedule of Study Assessments**

		Baseline	Interval/Data available per existing patient visits, medical charts						Study
Assessments	Screening		Time A	Time B	Time C	Time D	Time E	Time F, etc.	Completion/ Termination ^a
Informed Consent b	X					0			
Eligibility Criteria ^b	X				C				
Demographic Information		X							
AHA Information		X	X	X	X	X	X	X	
Medical History		X	X	X,C	X	X	X	X	
Concomitant Medications		X	X	X	X	X	X	X	X
Safety: SAEs		X	X	X	X	X	X	X	X
Laboratories (as available) c		X	X	X	X	X	X	X	X
Obizur Treatment Information		X	CX	X	X	X	X	X	X
Concurrent Bleeding Episodes		X	X ^d	X^{d}	X^d	X^d	X ^d	X^{d}	

- a Include for cases of withdrawal or discontinuation.
 b Occurs before start of data collection.
 c For laboratory assessments, see Table 2.
 d Only if additional bleeds occur.

Table 2. Clinical Laboratory Data Collection Clinical Laboratory Data Collection									
	c ·	D II	Interv	al/Data ava	Study				
Assessments	Screening	Baseline	Time A	Time B	Time C	Time D	Time E	Time F, etc.	Completion/Terminationa
Hematology*								11	
Hemoglobin		X							
Hematocrit		X							
CBC with differential, if consistent with local practice		X							
FVIII anti-human and anti-porcine antibodies±		X							

^{*}Given the observational nature of this study, data will be collected as recorded. No laboratory assessments are mandated by this Protocol.

[±] Baxalta will provide the option for physicians to use a central laboratory to process FVIII anti-human and anti-porcine antibodies

9.2.7 Subject Withdrawal and Discontinuation

Any subject may voluntarily withdraw (i.e., reduce the degree of participation in the study) consent for continued participation and data collection. The reason for withdrawal will be recorded on the End of Study CRF.

The data collected on withdrawn subjects will be used in the analysis and included in the non-interventional study report.

Discontinuation (i.e., complete withdrawal from study participation) may be due to dropout (i.e., active discontinuation by subject) or loss to follow-up (i.e., discontinuation by subject without notice or action). Additionally, the investigator and responsible party have the discretion to discontinue any subject from the study if, in their judgment,

continued participation would pose an unacceptable risk for the subject.

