Data collection will be limited to existing information and for the purposes of this study will be collected if data are (a) part of routine clinical practice or (b) elected by an investigator. Available data from patient visits shall be entered into an EDC system and checked for data quality. Keeping with the non-interventional study design, there will be no *required* visits, medical tests, laboratory tests and/or procedures, or interventions during the study duration. Baxalta will provide the option for physicians to use a central laboratory to process anti-human and anti-porcine FVIII antibodies, should they choose to do so.

If these assessments are made, it is recommended that a Bethesda assay using the Nijmegen modification be undertaken for antibodies measurement, and that pFVIII antibodies be tested before and during treatment administration, and in the follow-up. Lab results from local or other central laboratories available in the medical chart will be recorded; it is not a requirement of the study that these lab tests be completed.

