9.3.11 Subject Completion/Discontinuation

A subject is considered to have completed the study when he/she ceases active participation in the study because the subject has, or is presumed to have, completed the study according to the protocol.

Reasons for completion/discontinuation will be reported on the Completion/ Discontinuation CRF, including: completed, screen failure, AE (e.g., death), discontinuation by subject (e.g., lost to follow-up, dropout), study terminated by the MAH, or other (reason to be specified by the investigator). Regardless of the reason, all data available for the subject up to the time of completion/discontinuation should be recorded on the appropriate CRF and will be used in the analysis and included in the study report.

In the event of subject discontinuation due to an AE, clinical and/or laboratory investigations performed as part of the evaluation of the event will be reported to the MAH. Details of the outcome may be reported to the appropriate regulatory authorities by the responsible party.

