11.1.2 Assessment of Adverse Events

Each SAE from time of Obizur treatment until study completion will be described on the SAE CRF using the medical diagnosis (preferred), or, if no diagnosis could be established at the time of reporting the SAE, a symptom or sign, in standard medical terminology in order to avoid the use of vague, ambiguous, or colloquial expressions (see definitions in Section 11.1). For the purpose of this study only SAEs will be collected. Reasons for collecting SAEs only include: patients enrolled in this study are often elderly with a multitude of comorbidities and high medication intake. Additionally, they are seriously diseased receiving treatment in intensive care units. Thus, making qualified assessments of non-serious AEs with respect to isolated medicinal products is next to impossible given the multitude of treatments administered concomitantly. Each AE will be evaluated by the investigator for:

- Seriousness as defined in Section 11.1.1.1
- Severity as defined in Section 11.1.2.1
- Causal relationship to Obizur exposure as defined in Section 11.1.2.2

For each SAE, the outcome (i.e., recovering/resolving, recovered/resolved, recovered/resolved with sequelae, not recovered/not resolved, fatal, unknown) and if applicable action taken (i.e., dose increased, dose not changed, dose reduced, drug interrupted, drug withdrawn, not applicable, or unknown) will also be recorded on the AE CRF. Recovering/resolving SAEs will be followed until resolution, or 180 days post Obizur administration, which is first. If the severity rating for an ongoing SAE changes before the event resolves, the original SAE report will be revised (i.e., the event will not be reported as separate SAE). During the course of any SAE, the highest severity rating will be reported.

Any pregnancy that occurs after administration of medicinal product Obizur will be reported on a Pregnancy Form and followed-up at one year post-delivery, if feasible.

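### Subjects can be discontinued from this chart-based safety study for perceived risk or an AE, and nothing says that SAE collection then continues to day 180

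*Protocol*

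**What the plan says.** Protocol Section 9.2.7 gives the investigator and the responsible party a discretionary power to end any subject's participation. The test is whether, in their view, "continued participation would pose an unacceptable risk for the subject". The same section defines the term broadly: "Discontinuation (i.e., complete withdrawal from study participation"). This is an exit from the study, not only from Obizur.

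Section 9.3.11 gives the reasons to be entered on the CRF, among them "completed, screen failure, AE (e.g., death), discontinuation by subject (e.g., lost to follow-up, dropout"). Whatever the reason, the data available up to completion or discontinuation are recorded and analysed. It then adds a provision for AE exits, which opens "In the event of subject discontinuation due to an AE" and under which the MAH receives the results of the work-up of that event.

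Three other places bear on this:

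- Section 9.1 leaves the regimen to the treating physician and says that the study requires none of the following: "visits, medical tests, laboratory tests and/or procedures, or interventions during the study duration".
- Section 9.2.2 sets participation at 180 days for each qualifying bleed.
- Section 11.1.2 states: "Recovering/resolving SAEs will be followed until resolution, or 180 days post Obizur administration", whichever comes first. It does not mention discontinued subjects.

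**The concern.** In an interventional trial, a rule that takes a subject out for risk protects the subject from a study treatment or procedure. Here there is none. Obizur is chosen before and independently of enrollment, and data come from existing records. Taking a subject out therefore leaves care as it was and mainly stops the recording.

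The rule is also tied to the outcome being measured. The primary objective is the incidence of therapy-related SAEs, and the abstract gives longer-term safety to 180 days as a reason for the study. If an AE or a perception of rising risk can end observation, follow-up is shorter in subjects selected for safety reasons. Section 9.7.2 analyses available data without imputation, so what happens to them afterwards is simply absent.

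**Working it through.** **1. What is kept and what can be lost after a discontinuation**

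| Item | Position in the protocol |
|---|---|
| The SAE that led to discontinuation | Kept: recorded up to exit (9.3.11) and counted |
| Work-up of that event | Kept: reported to the MAH (9.3.11) |
| Later course of that event | Unclear: 11.1.2 follows recovering SAEs to resolution or 180 days but is silent on discontinued subjects |
| New SAEs after exit | Not addressed: 11.1.2 describes SAEs up to study completion and does not say what this means for a discontinued subject |
| Later death from another cause | Not addressed |
| Antibody titers after exit | Not addressed, although 9.3.6 collects them through 180 days |
| First related SAE in a subject removed for an unrelated AE or perceived risk | Not addressed |

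**2. The protocol's own precision figure**

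Inputs from Section 9.5: N = 40, 5% with a related event (x = 0.05 × 40 = 2), two-sided 95% Clopper-Pearson interval.

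Lower limit = Beta(0.025; x, N − x + 1); upper limit = Beta(0.975; x + 1, N − x).

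For x = 2 this gives 0.6% to 16.9%, as stated in Section 9.5.

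**3. Effect on the incidence proportion**

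Section 9.7.3 defines the proportion as patients with events over patients treated. Suppose 2 of 40 are observed, and k further subjects have a first related SAE after discontinuation that is not seen. The documents do not give k, so a range is shown. Each unit of k adds 1/40 = 2.5 points.

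| k | Proportion with complete follow-up | 95% interval |
|---|---|---|
| 0 | 2/40 = 5.0% | 0.6% to 16.9% |
| 1 | 3/40 = 7.5% | 1.6% to 20.4% |
| 2 | 4/40 = 10.0% | 2.8% to 23.7% |
| 4 | 6/40 = 15.0% | 5.7% to 29.8% |

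A subject discontinued because of a related SAE is already in the numerator and adds nothing to k.

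**4. Effect on the incidence rate**

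Section 9.7.3 also plans events per follow-up time. Assume two subjects each have one related SAE and are discontinued on day t, and the other 38 are followed for 180 days.

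- Person-years with discontinuation: (38 × 180 + 2t)/365.25. For t = 5 this is 18.75, and for t = 30 it is 18.89.
- Observed rate: 2/18.75 = 0.107 and 2/18.89 = 0.106 per person-year.
- Person-years with full follow-up: 40 × 180/365.25 = 19.71.
- Full-follow-up rate with 0, 1 or 2 further related events: 2/19.71 = 0.102 (0.1015 before rounding), 3/19.71 = 0.152, 4/19.71 = 0.203.

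With no further events, the rule makes the rate slightly too high, because person-time is lost. With one unseen event it makes the rate too low. The direction depends on what happens after exit, which is the information not collected.

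**The case against.** The strongest reply is that these are standard clauses with little practical reach. The test in Section 9.2.7 is risk from participation, not the occurrence of an AE. If participation is only chart abstraction, that test should hardly ever be met. The AE entry in Section 9.3.11 is a CRF category that does not direct anyone to remove a subject, and its one example, death, ends follow-up anyway. The sentence on data up to discontinuation requires data to be kept and used. Table 1 applies the completion/termination column, including SAEs and available laboratory results, to discontinued subjects. Section 11.1.2 has no exception for them and can be read as following their open SAEs to day 180.

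Much of this stands. It rules out two stronger readings that a reader might infer:

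- *That follow-up ends in exactly the patients with safety events, so that the study is biased towards a safe result.* The risk rule is discretionary and can reach event-free subjects, the triggering SAE is counted, and the rate can move either way.
- *That the loss can be sized from the planning range in Section 9.5.* Taking 5% to 15% of 40 as 2 to 6 subjects, each losing 170 of 180 days, gives 340 to 1,020 of 7,200 person-days (4.7% to 14.2%). This assumes that every subject with a related event is discontinued at day 10. Section 9.5 gives event proportions, and the documents state neither a discontinuation rate nor its timing.

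The reply does not remove the gap. Section 9.3.11 expressly foresees discontinuation due to an AE, so the route is open to sites. The SAE follow-up sentence in Section 11.1.2 covers events already under way, not new ones. A clause that should almost never apply gives no protection that would justify keeping it as a way to end observation.

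**Conclusion.** The concern holds in a limited form. The protocol permits complete discontinuation for perceived risk or an AE and does not say that SAE collection continues. That does not fit its 180-day participation period or its SAE follow-up rule. These provisions are not cross-referenced, and sites could act on them differently.

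The possible loss is confined to the later and unaddressed items in the table above. For the primary proportion, the size is 2.5 points per missed first related SAE among 40 subjects. The number of such events, and hence the total bias and the direction for the rate, cannot be derived from the documents. The figures for k and for exit on days 5 to 30 are illustrations under stated assumptions. The change is still worth making, because the study exists to describe safety to day 180 and the correction is cheap.

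**What to change.** Reconcile Sections 9.2.7, 9.3.11 and 11.1.2:

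- In 9.2.7, remove perceived risk as a reason to end observation.
- In 9.3.11, replace the AE entry in the list of reasons with death, and remove or reword the paragraph that begins "In the event of subject discontinuation due to an AE" so that a non-fatal AE is not a reason to leave the study.
- Add a statement, cross-referenced in 11.1.2, that an AE, an SAE or the end of Obizur treatment does not end study participation, and that chart-based SAE, outcome and vital-status data are collected to day 180 unless the subject dies, withdraws consent or is lost to follow-up.

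This concerns observation only. Treatment decisions stay with the treating physician, as now.

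The cost is a short wording change, one CRF pick-list edit and slightly more chart abstraction in a few subjects. No visit or test is added.

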9.2.8 Study Stopping Rules

Enrollment into the study will end if the following criteria are met:

1. At least 40 subjects have been enrolled in the prospective study.

9.3 Variables

9.3.1 Baseline subject information

- Demographics (age, sex, weight, race, ethnicity)
- Pregnant or breast-feeding

9.3.2 Medical history

- Bleed description
 - Spontaneous/traumatic, superficial/internal
 - Location: intramuscular, retroperitoneal, gastrointestinal, intracranial, specify
- Hematology laboratory results (baseline and any follow-up)
 - ➤ Hemoglobin [< 8g/dL, severe]
 - > Hematocrit
 - Complete blood count with differential.
 - ➤ Date of blood draw (include baseline and any follow-up)

- Bleed severity (severe/not severe)
 - Measured by physician
 - ➤ Hemoglobin levels [< 8, severe]
 - o Date of draw and results
- FVIII activity levels (baseline)
 - > Date of draw and results
- Anti-human and anti-porcine FVIII antibody titers (baseline)
 - > Date of draw and results
- Prior treatment with hemostatic agents (baseline)
 - > Regimen received
 - ➤ Medication start and stop dates (retrospective cohort only)
- Comorbidities (baseline)
 - List of all comorbidities with start dates
 - ➤ Physician relationship assessment (possibly associated with causation of AHA/not associated with AHA)
- Current medications not related to AHA (taken within 14 days)
 - Name of medication
 - Medication start/stop dates
 - Medication dose
- AHA diagnosis
 - Date
- Presentation of AHA symptoms
 - Symptom
 - Date

9.3.3 Medication during treatment

- Immunosuppressive agents received to treat underlying AHA
 - Dose and frequency
 - Date

9.3.4 Obizur Utilization

- Date and time of infusion
- Dose per infusion (U/kg)
- Total number of days of Obizur use

9.3.5 Safety (collect all SAEs; endpoint is therapy-related SAEs)

For the purpose of this study only serious adverse events (SAEs) will be collected. Reasons for collecting SAEs only include the following: Patients enrolled in this study are often elderly with a multitude of comorbidities and high medication intake. Additionally, they are seriously diseased receiving treatment in intensive care units. Thus, making qualified assessments of non-serious AEs with respect to isolated medicinal products is next to impossible given the multitude of treatments administered concomitantly.

- Key safety concerns:
 - > Inhibitor development against pFVIII (post baseline)
 - Date of inhibitor draw
 - > Hypersensitivity reactions including anaphylaxis
 - > Thrombogenicity
 - > Outcomes, including death (yes/no, date of death)

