8.2 Primary Objective

The primary objective is to determine the incidence of therapy-related SAEs in patients with AHA who are prescribed and treated with Obizur in routine clinical practice.

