9.1.1 Primary Outcome

The primary outcome is patient safety in terms of AEs, their seriousness and severity. In particular, describing:

• Incidence of therapy-related SAEs and level of severity

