9.1.2 Secondary Outcomes

Secondary outcomes will describe:

- Effectiveness assessment for resolution of bleeding, determined as either bleeding stopped or didn't stop
 - ➤ If bleeding did not stop, a reason should be provided (e.g., death)
- Time to bleeding resolution, death, or switch to another treatment.
- Number of Obizur units/kg required for control of bleeding (bleeding stopped)
- Number of Obizur infusions required for control of bleeding (bleeding stopped)
- Newly recognised anti-pFVIII inhibitors or increase in titer of anti-pFVIII
 inhibitors from pre-treatment level, impact on hemostatic efficacy and associated
 clinical manifestations if any, and evolution of titer over time
- Occurrence of hypersensitivity reactions
- Occurrence of any thrombogenic event

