9.7.3.1 Primary Outcome

The primary outcome (see Section 9.1.1) is patient safety in terms of AEs, their seriousness and severity. In particular, describing:

• Incidence of therapy-related SAEs and level of severity

These data will be described in tables and listings.

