11.1.2.1 Severity

The Investigator will assess the severity of each AE using his/her clinical expertise and judgment based on the most appropriate description below; only AEs considered serious will be reported in this study:

• Mild

- ➤ The AE is a transient discomfort and does not interfere in a significant manner with the subject's normal functioning level.
- ➤ The AE resolves spontaneously or may require minimal therapeutic intervention.

Moderate

- > The AE produces limited impairment of function and may require therapeutic intervention.
- ➤ The AE produces no sequela/saquelae.

Severe

- ➤ The AE results in a marked impairment of function and may lead to temporary inability to resume usual life pattern.
- ➤ The AE produces sequela/sequelae, which require (prolonged) therapeutic intervention.

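### The hypersensitivity outcome has no seriousness limit, but the protocol collects only serious events, so the reported occurrence can equal or understate the stated outcome and never exceed it

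*Protocol*

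**What the plan says.** **What is to be reported.** Section 9.1.2 lists "Occurrence of hypersensitivity reactions" among the secondary outcomes, and 9.7.3.2 repeats it in the analysis section. Neither place limits it to serious reactions. Section 9.3.5 puts hypersensitivity among the key safety concerns and mentions anaphylaxis as one form of it, so milder forms are within its meaning.

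**What is to be collected.** Section 9.3.5 states: "For the purpose of this study only serious adverse events (SAEs) will be collected". Section 11.1.2 says the same ("For the purpose of this study only SAEs will be collected"), and 11.1.2.1 adds that "only AEs considered serious will be reported in this study". In Table 1 (section 9.2.6) the only safety-event row is for SAEs. The reason given in 9.3.5 and 11.1.2 is that these patients are often elderly, very ill and on many treatments at once, so that non-serious events can hardly be assessed against a single product.

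**The primary measure.** Section 8.2 reads: "The primary objective is to determine the incidence of therapy-related SAEs in patients with AHA". Sections 9.1.1 and 9.7.3.1 open more broadly ("The primary outcome is patient safety in terms of AEs, their seriousness and severity"), but both then narrow to "Incidence of therapy-related SAEs and level of severity".

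**The concern.** A secondary outcome defined on all hypersensitivity reactions is to be filled from a data stream confined to serious ones. Section 11.1.1 itself gives rash as an example of an adverse event. A rash after an infusion that meets no seriousness criterion is a hypersensitivity reaction for 9.1.2 but falls outside collection under 9.3.5.

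This is a post-authorization safety study, and hypersensitivity is one of the few concerns it singles out. A low figure under the label in 9.1.2 would naturally be read as the frequency of all reactions. A later analysis plan cannot repair this, because it cannot analyse events that sites were told not to record.

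**Working it through.** **Step 1. Capture route for each key safety concern in 9.3.5.**

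| Concern | Route other than general SAE reporting | Explicitly placed within SAEs? |
|---|---|---|
| Inhibitors to porcine FVIII | Dated titers through 180 days (9.3.6); date of draw (9.3.5) | Not needed |
| Thrombogenicity | None | Yes: thrombotic and embolic events are an example of a medically important event (11.1.1.1) |
| Death | Own item with date (9.3.5) | Yes: a seriousness criterion (11.1.1.1) |
| Hypersensitivity | None stated | Only in part: the one allergic example is intensively treated bronchospasm (11.1.1.1) |

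Hypersensitivity is the only one of the four with neither its own data item nor a general placement among SAEs.

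**Step 2. Direction.** Let p be the proportion of subjects with any hypersensitivity reaction, and s the share of those subjects with at least one reaction meeting an SAE criterion. The recorded proportion is p × s. Since s is at most 1, p × s is at most p. The direction follows from the design and needs no outside figure.

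**Step 3. Reproduce the plan's own precision figure.** Section 9.5 uses the exact (Clopper-Pearson) method. With x events in n subjects:

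- lower limit = 2.5% quantile of Beta(x, n − x + 1)
- upper limit = 97.5% quantile of Beta(x + 1, n − x)

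For n = 40 and 5% (x = 2) this gives 0.6% to 16.9%, as 9.5 states. The other table rows agree within 0.1 percentage point. For example, the 10% row prints a lower limit of 2.7% where the recomputation gives 2.8%.

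**Step 4. Illustration of size.** The documents give neither p nor s, so every input here except n = 40 is an assumption. Take 4 of 40 subjects reacting (p = 10%).

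| Assumed subjects with a serious reaction | Reported proportion | Exact 95% CI |
|---|---|---|
| 4 (all captured) | 10% | 2.8% to 23.7% |
| 2 (s = 50%) | 5% | 0.6% to 16.9% |
| 1 (s = 25%) | 2.5% | 0.1% to 13.2% |

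The chance that at least one affected subject appears in the data is 1 − (1 − p × s)^40:

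| Assumed p | s = 100% | s = 50% | s = 25% | s = 10% |
|---|---|---|---|---|
| 5% | 87.1% | 63.7% | 39.5% | 18.2% |
| 10% | 98.5% | 87.1% | 63.7% | 33.1% |
| 15% | 99.8% | 95.6% | 78.3% | 45.4% |

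The spread of this table is itself a result: the loss could be small or large, and the documents cannot say which.

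**The case against.** **SAE-only collection is a disclosed and reasoned choice.** It is stated three times with its rationale, and hypersensitivity is listed under the SAE heading of 9.3.5. A careful reader could take the outcome to mean reactions captured as SAEs. This stands as a defence of SAE-only collection in general, and I do not dispute it. It does not settle the outcome as worded in 9.1.2 and 9.7.3.2. The rationale is also about attributing events to one product, whereas occurrence can be described without attribution, and 9.3.4 already records the date and time of each infusion. An infusion time does not rule out other drugs given in the same window, so the attribution difficulty itself remains.

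**The SAE definition is broad.** Section 11.1.1.1 includes events that prolong hospitalization and medically important events that may need intervention to prevent a worse outcome, and its list is only of examples. This stands: clinically important reactions should qualify, and what is lost would be mainly the milder, self-limited ones.

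**A reader might infer that non-serious reactions have no place on any form.** The documents do not establish that. The case report forms are not shown. Section 9.3.8 sends new or worsened abnormal conditions found at follow-up examination to the SAE form without repeating the seriousness condition, and 9.3.7 records all medications to completion. These provisions leave some ambiguity, but none clearly tells a site to record a non-serious reaction, and a broad reading of 9.3.8 would conflict with 9.3.5 and 11.1.2.

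**A reader might also infer that the primary outcome cannot be produced**, because 9.7.3.1 says it "is patient safety in terms of AEs, their seriousness and severity". The documents do not support this. The primary objective in 8.2, the specific measure in 9.1.1 and 9.7.3.1, the heading of 9.3.5 and the analysis in 9.7.3 all use therapy-related SAEs, which SAE-only collection supplies in full.

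**Conclusion.** The point holds for the secondary hypersensitivity outcome alone. As written, the protocol would report reactions that meet an SAE criterion under a label covering all reactions, so the figure can only equal or understate the stated outcome. That direction rests on two things: sites follow the SAE-only instruction, and no unseen form captures non-serious reactions.

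The amount of understatement cannot be derived. A fall from 10% to 2.5% is one assumed case, and its two intervals (2.8% to 23.7% and 0.1% to 13.2%) overlap widely. The outcome is descriptive, with no hypothesis test, so what is at stake is how a safety frequency is interpreted. The primary endpoint is not biased by this, and the broad opening sentence in 9.1.1 and 9.7.3.1 is a wording matter only.

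**What to change.** **Preferred.** Keep SAE-only collection for everything else. State in 9.3.5, 11.1.2, 11.1.2.1 and Table 1 that hypersensitivity and infusion reactions documented in the chart are recorded regardless of seriousness, with onset, timing relative to the infusion, severity and seriousness. Report all reactions and the serious subset separately. The cost is a short form and a small amount of extra chart abstraction. No visit, test or procedure is added, so the non-interventional design in 9.1 is preserved.

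**If declined.** Restate the outcome in 9.1.2 and 9.7.3.2 as hypersensitivity reactions meeting SAE criteria, and use that label in every report. This costs a wording change only, and it gives up any statement about non-serious reactions.

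**Either way.** Make clear in 9.3.8 whether the SAE form is limited to serious conditions. As a tidy-up, align the opening sentence of 9.1.1 and 9.7.3.1 with therapy-related SAEs and their severity.
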